7.0 Protocol Treatment

7.1 Treatment Schedule

Agent	Dose Level	Route	Day
Pazopanib	800 mg	PO	once daily

Cycle length=28 days

Protocol treatment consists of four 200mg tablets (800 mg) of pazopanib by mouth once a day.

7.13 GW786034

Pazopanib monohydrochloride salt is supplied as aqueous film-coated tablets containing 200 mg of the free base. The 200-mg tablets are oval-shaped and gray in color. Refer to the pazopanib IB for information regarding the physical and chemical properties of pazopanib and a list of excipients.

Pazopanib will be provided to the sites by Novartis. The 200-mg pazopanib tablets are packaged 34 to a bottle. Bottles are made of high-density polyethylene and have a child-resistant closure. Each bottle will be labeled with the protocol number, dosing and storage instructions, sponsor name and address, and the expiration date, when required. The contents of the label will be in accordance with all applicable regulatory requirements.

7.12 Dosage and Administration

Administration of pazopanib with a high-fat or low-fat meal results in an approximately 2-fold increase in area under the plasma drug concentration curve (AUC) and maximum observed plasma drug concentration (C_{max}).

Pazopanib should be taken orally without food at least one hour before or two hours after a meal. The tablets should be swallowed whole and must not be crushed or broken. The time of day the tablets are taken should be relatively constant.

If a dose is missed, the subject should take the dose as soon as possible, but only if there are 12 or more hours remaining before the next dose is due. If the next dose is due in less than 12 hours, the subject should skip the missed dose and take the next dose as scheduled.

If vomiting occurs after taking pazopanib, the subject should not take a replacement dose on that day. The subject should resume taking pazopanib at the next scheduled dose on the following day. If vomiting persists, the subject should be instructed to notify the investigator.

As a general rule, if dose reduction of pazopanib is necessary, the dose should be reduced stepwise by 200 mg at each step, and the subject should be monitored for approximately 10 to 14 days at each dose level. If toxicity does not abate during this monitoring time, the medication may need to be interrupted and/or the dose further decreased with continued monitoring for an additional 10-14 days at each dose level, and so on.

If the toxicity has abated with reduction of the dose and dose re-escalation is considered safe by the investigator, the dose can then be increased step-wise back to the pre-event dose (in 200 mg increments, after monitoring for 10-14 days at each dose level to ensure that toxicity did not recur or worsen).

If a subject's treatment has been interrupted for more than 21 days, the Investigator must contact the Study Physician to review the subject's condition in order to resume the treatment.

- 7.2 Patients can be instructed in administration techniques and granted treatment independence with nursing staff approval.
- 7.3 For this protocol, the patient must return to Mayo Rochester, Florida, or Arizona for evaluation at least every 28 days (+/- 3 days).

7.4 Criteria for Treatment Discontinuation

- Patients who develop PD/recurrent disease while receiving therapy at the time of response assessments will be discontinued from active study treatment and go off protocol;
- Grade 3 or 4 toxicity requiring break from treatment and inability to re-initiate treatments with a ≥ 28 day delay;
- Completion of 12 months of therapy.

8.0 Dosage Modification Based on Adverse Events

8.1 Pazopanib

8.11 Pazopanib Dose Reduction Levels

Starting Dose	800 mg once daily
Dose Level -1	600 mg once daily
Dose Level -2	400 mg once daily

8.12

→ → Use the NCI Common Terminology Criteria for Adverse Events (CTCAE) version 4.0* unless otherwise specified ← ←			
CTCAE System/Organ/Class (SOC)	ADVERSE EVENT	AGENT	ACTION**
BASED ON INTERVAL ADVERSE EVENT			
Investigations	Platelet count decreased Grade 3 or 4	Pazopanib	Omit until ≤ 2 then restart at next lower dose level. If no recovery to grade 2, discontinue
Investigations	Electrocardiogram QT corrected interval prolonged ≥ 500 msec Grade 3	Pazopanib	Discontinue pazopanib
Renal and urinary disorders	Creatinine \geq Grade 3	Pazopanib	Omit until < 3 then restart at next lower dose level. If ≥ 3 recurs, reduce one dose level again until no dose can be given

→ → Use the NCI Common Terminology Criteria for Adverse Events (CTCAE) version 4.0* unless otherwise specified ← ←			
CTCAE System/Organ/Class (SOC)	ADVERSE EVENT	AGENT	ACTION**
Vascular disorders	Thromboembolic event DVT/PE Grade 3	Pazopanib	Omit and initiate anticoagulant. Restart at reduced dose if 
 • Subject must have been treated at desired level of anticoagulation for at least 1 week • No Grade 3 or 4 or clinically significant Grade 2, hemorrhagic events have occurred while on anticoagulation treatment. Note: When treating with warfarin, INR S/B monitored within 3 to 5 days after any change in pazopanib dosing and then at least weekly until INR is stable. The dose of warfarin may need to be adjusted to maintain the desired level of anticoagulation.
	Grade 4 Arterial Thrombosis/Ischemia Any Grade		Discontinue pazopanib Discontinue pazopanib
Vascular disorders	Hypertension	Pazopanib	See table 8.2
Gastrointestinal disorders	Any GI bleed Grade 2-4	Pazopanib	Discontinue pazopanib
Respiratory, thoracic and mediastinal disorders	Any Pulmonary bleed Grade 2-4	Pazopanib	Discontinue pazopanib
Dermatology/ Skin	Dermatitis Grade 2 skin changes w/pain, limiting ADL's Grade3 severe skin changes w/pain Limiting self care ADL's	Pazopanib	Omit until ≤ 1 , then restart at next lower dose level. If recurrent, reduce by another dose level or discontinue Discontinue

→ → Use the NCI Common Terminology Criteria for Adverse Events (CTCAE) version 4.0* unless otherwise specified ← ←			
CTCAE System/Organ/Class (SOC)	ADVERSE EVENT	AGENT	ACTION**
All Other	Grade 2 or 3, if clinically significant Grade 4	Pazopanib	Omit until ≤ 1 Discontinue Pazopanib

* Located at

http://ctep.cancer.gov/protocolDevelopment/electronic_applications.ctc.htm

** Use the following to describe actions in the Action column:

- Omit = Treatment is not given for this cycle
- Hold/Delay = Treatment can be made up as part of this cycle
- Discontinue = Treatment is totally stopped

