8.2 Pazopanib-at time of retreatment

→ → Use the NCI Common Terminology Criteria for Adverse Events (CTCAE) version 4.0* unless otherwise specified ← ←			
CTCAE System/Organ/Class (SOC)	ADVERSE EVENT	AGENT	ACTION**
AT TIME OF RETREATMENT			
Investigations	Platelet count decreased Grade 3 or 4	Pazopanib	Hold until ≤ 2 then restart at next lower dose level. If no recovery to grade 2, discontinue
Investigations	Electrocardiogram QT corrected interval prolonged ≥ 500msec Grade 3	Pazopanib	Discontinue pazopanib
Renal and urinary disorders	Creatinine > Grade 3	Pazopanib	Hold until < 3 then restart at next lower dose level. If ≥ 3 recurs, dose reduce again until no dose can be given

→ → Use the NCI Common Terminology Criteria for Adverse Events (CTCAE) version 4.0* unless otherwise specified ← ←			
CTCAE System/Organ/Class (SOC)	ADVERSE EVENT	AGENT	ACTION**
Vascular disorders	Thromboembolic event DVT/PE Grade 3	Pazopanib	Hold and initiate anticoagulant. Decrease 1 dose level if 
 • Subject must have been treated at desired level of anticoagulation for at least 1 week • No Grade 3 or 4 or clinically significant Grade 2, hemorrhagic events have occurred while on anticoagulation treatment. Note: When treating with warfarin, INR S/B monitored within 3 to 5 days after any change in pazopanib dosing and then at least weekly until INR is stable. The dose of warfarin may need to be adjusted to maintain the desired level of anticoagulation.
	Grade 4		Discontinue pazopanib
	Arterial Thrombosis/Ischemia Any Grade		Discontinue pazopanib
Vascular disorders	Hypertension	Pazopanib	See table 8.3
Gastrointestinal disorders	Any GI bleed Grade 2-4	Pazopanib	Discontinue pazopanib
Respiratory, thoracic and mediastinal disorders	Any Pulmonary bleed Grade 2-4	Pazopanib	Discontinue pazopanib
Dermatology/ Skin	Dermatitis Grade 2 skin changes w/pain, limiting ADL's Grade3 severe skin changes w/pain Limiting self care ADL's	Pazopanib	Hold until ≤ 1 , then restart at next lower dose level. If recurrent. reduce by another dose level or discontinue Discontinue

→ → Use the NCI Common Terminology Criteria for Adverse Events (CTCAE) version 4.0* unless otherwise specified ← ←			
CTCAE System/Organ/Class (SOC)	ADVERSE EVENT	AGENT	ACTION**
All Other	Grade 2 or 3, if clinically significant Grade 4	Pazopanib	Hold until ≤ 1 Discontinue pazopanib

* Located at

http://ctep.cancer.gov/protocolDevelopment/electronic_applications.ctc.htm

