Grade 1	For hemoptysis, interrupt pazopanib and contact the Novartis Study Physician to discuss whether further treatment with pazopanib is appropriate. For other Grade I hemorrhage/bleeding events, continue pazopanib at the current dose; monitor as clinically indicated.
Grade 2	Step 1. If pulmonary or GI bleed (other than hemorrhoidal bleeding), discontinue pazopanib and continue follow-up per protocol. Otherwise, interrupt pazopanib until the AE resolved to \leq Grade 1. Step 2. Restart pazopanib ; consider reducing dose and monitor as clinically indicated.
Grade 3 or 4, or Recurrent \geq Grade 2 event after dose interruption/reduction.	Discontinue pazopanib and continue with follow-up per protocol.
Venous Thrombosis (DVT, PE)	
Grade 2	Continue pazopanib at the current dose; monitor as clinically indicated
Grade 3	Step 1. Interrupt pazopanib . Step 2. Initiate and monitor anticoagulation as clinically indicated. Step 3. Resume pazopanib at reduced dose only if all of the following criteria are met: 
 • The subject must have been treated with anticoagulant at the desired level of anticoagulation for at least one week. • No Grade 3 or 4 or clinically significant Grade 2, hemorrhagic events have occurred while on anticoagulation treatment. Subject should be monitored as clinically indicated during anticoagulation treatment and after resuming study treatment. When treating with warfarin, international normalized ratio (INR) should be monitored within three to five days after any change in pazopanib dosing (eg, re-initiating, escalating/de-escalating, or discontinuing pazopanib), and then at least weekly until the INR is stable. The dose of warfarin (or its derivatives) may need to be adjusted to maintain the desired level of anticoagulation
Grade 4 and/or PE	Discontinue pazopanib and continue follow-up per protocol.
Arterial Thrombosis/Ischemia	
Any Grade	Discontinue pazopanib and continue follow-up per protocol.
Thrombocytopenia: Investigate and document underlying cause	
Grade 1 or 2	Continue pazopanib with current dose; monitor as clinically indicated.
Grade 3 or 4	Step 1. Interrupt pazopanib until toxicity resolves to \leq Grade 2.

	Step 2. Restart pazopanib dose-reduced by 200 mg and monitor as clinically indicated. If no recovery to \leq Grade 2 or recurrent Grade 3 or 4 thrombocytopenia, discontinue IP and follow-up per protocol.

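### After a grade 3 pulmonary embolism, Sections 8.12 and 8.2 restart pazopanib at a reduced dose while Section 8.3 stops it for good, and no text says which governs

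*Combined protocol and SAP*

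**What the plan says.** Three tables in Section 8 give an action for PE.

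- **Section 8.12** (events during a cycle) has a row "Thromboembolic event DVT/PE Grade 3". Its action is "Omit and initiate anticoagulant. Restart at reduced dose if" two conditions are met: at least a week of anticoagulation at the intended level, and no grade 3 or 4 bleeding (or clinically important grade 2 bleeding) while on it. Grade 4 events are discontinued.
- **Section 8.2** (at retreatment) has the same row and the same conditions: "Hold and initiate anticoagulant. Decrease 1 dose level if". Grade 4 is again discontinued.
- **Section 8.3** has a venous thrombosis block. Its grade 3 row says "Resume pazopanib at reduced dose only if all of the following criteria are met", with the same two conditions. The next row, "Grade 4 and/or PE", discontinues pazopanib and keeps the patient in follow-up.

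The key under 8.12 and 8.2 defines discontinuation as a complete stop. It distinguishes this from omitting a drug for the cycle and from holding it.

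On the liver, Section 8.4 stops pazopanib for raised ALT with raised bilirubin only when the direct fraction exceeds 35%, or when there are hypersensitivity symptoms. Sections 15.15(c) and 15.28 call for permanent discontinuation when AST or ALT is above 3 x ULN and bilirubin is above 2 x ULN, with no condition on the direct fraction.

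**The concern.** A grade 3 PE on a VEGF-pathway inhibitor is a serious event, and the protocol expects such events: Section 15.26 asks nurses to watch for thrombosis and PE. The investigator needs one answer on whether the drug may be given again. Here a site using 8.12 or 8.2 would anticoagulate and restart at a lower dose, while a site using 8.3 would stop for good. Both would be following the protocol. At stake are the safety of the re-exposed patient and uniform dosing across the three Mayo sites. The primary endpoint is not at stake: Section 16.11 counts every eligible patient who began treatment, and Section 13.3 moves patients who stop treatment into event monitoring.

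**Working it through.** No design formula is involved. The check sets the rules side by side and then asks whether anything else in the protocol chooses between them.

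**Step 1. Same patient, three tables.** Take a PE, anticoagulated at target for at least a week, without significant bleeding.

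| Table | Grade 3 PE | Grade 4 PE |
|---|---|---|
| 8.12 | omit, then restart at reduced dose | discontinue |
| 8.2 | hold, then restart one level down | discontinue |
| 8.3, last venous thrombosis row | discontinue | discontinue |

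The tables agree at grade 4 and contradict each other at grade 3.

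**Step 2. Does any text rank the tables?** The only pointers from 8.12 or 8.2 to another dose table are on the hypertension rows. The thromboembolic rows have none, and there is no general precedence statement.

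**Step 3. Do other rules settle it?**

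- Section 7.4 withdraws patients for "Grade 3 or 4 toxicity requiring break from treatment and inability to re-initiate treatments with a" delay of 28 days or more. Section 7.12 requires contact with the Study Physician after more than 21 days of interruption.
- Under 8.2 the hold can end after 7 days of anticoagulation, inside both limits.
- Under 8.12 an omission runs for the rest of the 28-day cycle. If the drug stops on cycle day *d*, the days omitted are 29 − *d*: 28 for *d* = 1, 21 for *d* = 8, and 7 for *d* = 22. For *d* from 8 to 22 the omission lasts 7 to 21 days. That is long enough for the one-week condition (assuming target anticoagulation is reached on the day of the event) and too short to trigger either rule.
- Where the omission is longer, 7.12 asks only for a discussion, and 7.4 applies only if treatment cannot be resumed.

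Neither rule decides the matter.

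**Step 4. Which rule fits the rest of the protocol?** Exclusion 3.26 lists PE and untreated DVT with a 6-month window. Its note admits patients with recent DVT after at least 6 weeks of therapeutic anticoagulation and has no counterpart for PE. The protocol therefore already treats PE more strictly than DVT, as 8.3 does.

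**Step 5. How many patients?** No rate for grade 3 PE is given. For venous thromboembolism of any kind in renal cell carcinoma, Section 15.17 says common (1% to under 10%) and Appendix VIII Table 78 says uncommon. I assume Table 78 uses the 15.17 definition of uncommon, 0.1% to under 1%. With 35 evaluable and 39 accrued patients:

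- lowest: 0.001 x 35 = 0.035
- highest: below 0.10 x 39 = 3.9

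Grade 3 PE is some part of this range.

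**Step 6. Secondary liver check** (illustrative values, no hypersensitivity symptoms, no Gilbert's syndrome).

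| ALT (x ULN) | Total bilirubin (x ULN) | Direct fraction | 8.4 | 15.15(c) and 15.28 |
|---|---|---|---|---|
| 5 | 2.5 | 30% | (B) continue | discontinue |
| 10 | 2.5 | 30% | (C) interrupt, re-challenge possible | discontinue |
| 5 | 2.5 | 40% | (D) discontinue | discontinue |

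The mismatch is confined to a direct fraction of 35% or less. Section 15 is also triggered by AST, whereas the 8.4 triggers name ALT only.

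**The case against.** The strongest reply is that a careful reader would follow the most specific instruction, the PE row in 8.3, and stop. That is the natural reading of 8.3, but it does not remove the conflict, because 8.12 and 8.2 also name PE in their grade 3 rows. A related reply is that 8.3 is titled for potentially treatment-related events. Nothing limits 8.12 and 8.2 to unrelated events, so a related PE still falls under both rules. It is fair that the restart is guarded by anticoagulation and bleeding conditions, that affected patients will be few, and that stopping after every PE is a clinical choice the study team must own.

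Three stronger readings are tempting but not supported.

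- **That 8.3 on its own supports either answer**, because its block heading names PE above the rows that keep the drug. A specific row ordinarily controls over a heading, so 8.3 is best read as stopping for any PE.
- **That a grade 2 PE is a second conflict**, because the 8.3 grade 2 row says "continue pazopanib at the current dose; monitor as clinically indicated" and 8.12 and 8.2 have no grade 2 thromboembolic row. Both of those tables have a catch-all row for clinically significant grade 2 or 3 events. Whether a PE can be graded 2 at all depends on CTCAE v4.0, which the documents do not reproduce.
- **That the absence of PE from 7.4 shows restart was intended.** Section 7.4 also omits arterial thrombosis and gastrointestinal bleeding, and 8.12 discontinues for both.

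On the liver, a reader might see a conflict of equal weight. Section 8.4 is the dedicated hepatotoxicity rule and Section 10.51 repeats its direct-fraction condition. Section 15.15(c) is a pharmacokinetic paragraph and 15.28 is nursing guidance, with an exception for mild hyperbilirubinemia in suspected or known Gilbert's syndrome. The remark in 8.4 about indirect bilirubin concerns isolated elevation without raised ALT, so it does not show that the combined case is frequent.

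**Conclusion.** The plan is wrong as written for grade 3 PE: two tables direct a conditional restart, a third directs permanent discontinuation, and nothing in the protocol chooses between them. This rests on reading discontinuation in 8.3 as a complete stop. The key to 8.12 and 8.2 defines it so, and 8.3 uses interruption for temporary stops. The consequence is for patient safety and consistent dosing; sample size, type I error, power and the 12-month survival analysis are unaffected. The number of patients is unknown and probably small: the range of 0.04 to fewer than 4 covers all venous thromboembolism, not grade 3 PE. It should be fixed because the instructions are opposite, the event is serious and the correction is cheap. The liver mismatch is a minor secondary note, mainly unaligned wording in Section 15, and no count can be given because Table 79 does not cross ALT with bilirubin or report the direct fraction.

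**What to change.** **PE.** In 8.12 and 8.2, change the grade 3 thromboembolic row to *DVT Grade 3* and add a row *PE: discontinue pazopanib*. In 8.3, mark the grade 2 and grade 3 venous thrombosis rows *DVT only* and reword the last row as *Grade 4 DVT, or any PE*. The study team should confirm the stricter 8.3 rule before it is adopted.

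**Liver.** Align 15.15(c) and 15.28 with 8.4 without losing the AST trigger, for example by adding AST to the 8.4 triggers in the same amendment. The reporting table in 10.51 repeats the ALT criteria and should be checked against the revised 8.4. The separate caution in 15.15(c) on total bilirubin above 3 x ULN stays.

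**Cost.** One wording amendment and a notice to three sites, with no change to sample size, visits, tests or analysis. The price of the PE rule is that some anticoagulated patients lose the option to restart. The price of following 8.4 on the liver is that some patients whom Section 15 would stop remain on drug, or may be re-challenged, under its monitoring.

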8.2 Pazopanib-at time of retreatment

→ → Use the NCI Common Terminology Criteria for Adverse Events (CTCAE) version 4.0* unless otherwise specified ← ←			
CTCAE System/Organ/Class (SOC)	ADVERSE EVENT	AGENT	ACTION**
AT TIME OF RETREATMENT			
Investigations	Platelet count decreased Grade 3 or 4	Pazopanib	Hold until ≤ 2 then restart at next lower dose level. If no recovery to grade 2, discontinue
Investigations	Electrocardiogram QT corrected interval prolonged ≥ 500msec Grade 3	Pazopanib	Discontinue pazopanib
Renal and urinary disorders	Creatinine > Grade 3	Pazopanib	Hold until < 3 then restart at next lower dose level. If ≥ 3 recurs, dose reduce again until no dose can be given

→ → Use the NCI Common Terminology Criteria for Adverse Events (CTCAE) version 4.0* unless otherwise specified ← ←			
CTCAE System/Organ/Class (SOC)	ADVERSE EVENT	AGENT	ACTION**
Vascular disorders	Thromboembolic event DVT/PE Grade 3	Pazopanib	Hold and initiate anticoagulant. Decrease 1 dose level if 
 • Subject must have been treated at desired level of anticoagulation for at least 1 week • No Grade 3 or 4 or clinically significant Grade 2, hemorrhagic events have occurred while on anticoagulation treatment. Note: When treating with warfarin, INR S/B monitored within 3 to 5 days after any change in pazopanib dosing and then at least weekly until INR is stable. The dose of warfarin may need to be adjusted to maintain the desired level of anticoagulation.
	Grade 4		Discontinue pazopanib
	Arterial Thrombosis/Ischemia Any Grade		Discontinue pazopanib
Vascular disorders	Hypertension	Pazopanib	See table 8.3
Gastrointestinal disorders	Any GI bleed Grade 2-4	Pazopanib	Discontinue pazopanib
Respiratory, thoracic and mediastinal disorders	Any Pulmonary bleed Grade 2-4	Pazopanib	Discontinue pazopanib
Dermatology/ Skin	Dermatitis Grade 2 skin changes w/pain, limiting ADL's Grade3 severe skin changes w/pain Limiting self care ADL's	Pazopanib	Hold until ≤ 1 , then restart at next lower dose level. If recurrent. reduce by another dose level or discontinue Discontinue

→ → Use the NCI Common Terminology Criteria for Adverse Events (CTCAE) version 4.0* unless otherwise specified ← ←			
CTCAE System/Organ/Class (SOC)	ADVERSE EVENT	AGENT	ACTION**
All Other	Grade 2 or 3, if clinically significant Grade 4	Pazopanib	Hold until ≤ 1 Discontinue pazopanib

* Located at

http://ctep.cancer.gov/protocolDevelopment/electronic_applications.ctc.htm

** Use the following to describe actions in the Action column:

- Omit = Treatment is not given for this cycle
- Hold/Delay = Treatment can be made up as part of this cycle
- Discontinue = Treatment is totally stopped

8.3 Dose Modification Algorithms for Potential Treatment-Related Adverse Events

AE Terms & Descriptions	Dose Modification Algorithms
Hypertension	
Scenario A) 
 • Asymptomatic and persistent^d SBP of ≥140 and <160 mmHg, or DBP ≥90 and <100 mmHg, or 
 • Clinically significant increase in DBP of 20 mmHg (but still below 110 mmHg). 	
 • Continue pazopanib treatment at the current dose • Adjust current or initiate new antihypertensive medication • Titrate antihypertensive medication(s) during the next 2 weeks as indicated to achieve well-controlled^b BP • If BP is not well controlled within 2 weeks, consider referral to a specialist and go to scenario (B).
(Scenario B) 
 • Asymptomatic SBP ≥160 mmHg, or DBP ≥100 mmHg, or 
 • Failure to achieve well-controlled BP within 2 weeks in Scenario A 	
 • Interrupt pazopanib treatment if clinically indicated • Adjust current or initiate new antihypertensive medication(s) • Titrate antihypertensive medication(s) during the next 2 weeks as indicated to achieve well-controlled BP • Once BP is well controlled^e, restart pazopanib treatment reduced by one dose level
or 
 • Symptomatic^f hypertension or 
 • Persistent^g SBP ≥160 mmHg, or DBP ≥100 mmHg, despite antihypertensive medication and dose reduction of study treatment 	
 • Interrupt pazopanib treatment • Adjust current or initiate new antihypertensive medication(s) • Titrate antihypertensive medication during the next 2 weeks as indicated to achieve well-controlled BP • Referral to a specialist for further evaluation and follow-up is recommended • Once BP is well controlled, restart pazopanib treatment reduced by one dose level

Refractory hypertension unresponsive to above interventions.	
 • Permanently discontinue pazopanib treatment • Continue follow-up per protocol.
LVEF-drop (%) or CTCAE grade	Action and Dose Modification
Asymptomatic: Absolute decrease of >10% in LVEF compared to baseline and ejection fraction below the institution's LLN OR LVEF drop >15% from baseline regardless of whether value is below institution's LLN.	
 • Interrupt pazopanib study treatment and repeat ECHO within 2 weeks^b and monitor and control BP. • If the LVEF recovers within 4 weeks (defined as LVEF \geqLLN and absolute decrease \leq10% compared to baseline) 
 ○ Restart study treatment^f reduced by one dose level (Please consult with Novartis if there are any questions prior to restarting) ○ Repeat ECHO 2, 4, 8 and 12 weeks after re-start; monitor BP; continue in intervals of 12 weeks thereafter • If repeat LVEF does not recover within 4 weeks 
 ○ Consult with cardiologist ○ Permanently discontinue pazopanib treatment Repeat ECHO after 2, 4, 8, 12, and 16 weeks or until resolution 
Please Consult with Novartis if there are any questions

Symptomatic ^c : Grade 3: resting LVEF 39-20% or >20% absolute reduction from baseline	
 • Permanently discontinue pazopanib treatment • Consult with cardiologist • Repeat ECHO after 2, 4, 8, 12, and 16 weeks or until resolution
Symptomatic ^c : Grade 4: resting LVEF <20%	
Prolongation of QTc Interval: If the QTc is prolonged, the ECG should be manually read to ensure accuracy of the reading. The values below refer to manually-read ECGs. REFER READER TO ECG SECTION IN PROTOCOL	
QTc \geq 480 < 500 msec	Continue pazopanib; monitor as clinically indicated.
QTc \geq 500 msec	Discontinue pazopanib and continue follow-up per protocol.
Proteinuria	
UPC <3	Continue pazopanib at the current dose; monitor as clinically indicated
UPC \geq 3 or 24-h urine protein \geq 3g	
Step 1. Interrupt pazopanib.
 
Step 2. Weekly UPC or 24-hr urine protein monitoring until UPC is <3 or 24-hr urine protein is <3 grams. Then restart pazopanib dose-reduced by 200 mg.
 
Step 3. If UPC \geq3 or 24-h urine protein \geq3g recurs, repeat steps 1 and 2.
 
Step 4. If UPC \geq3 or 24-hr urine protein \geq3 recurs and the pazopanib dose can no longer be reduced, discontinue pazopanib and continue follow-up per protocol.

Hemorrhage /Bleeding: Investigate and document underlying etiology of the bleeding	

Grade 1	For hemoptysis, interrupt pazopanib and contact the Novartis Study Physician to discuss whether further treatment with pazopanib is appropriate. For other Grade I hemorrhage/bleeding events, continue pazopanib at the current dose; monitor as clinically indicated.
Grade 2	Step 1. If pulmonary or GI bleed (other than hemorrhoidal bleeding), discontinue pazopanib and continue follow-up per protocol. Otherwise, interrupt pazopanib until the AE resolved to \leq Grade 1. Step 2. Restart pazopanib ; consider reducing dose and monitor as clinically indicated.
Grade 3 or 4, or Recurrent \geq Grade 2 event after dose interruption/reduction.	Discontinue pazopanib and continue with follow-up per protocol.
Venous Thrombosis (DVT, PE)	
Grade 2	Continue pazopanib at the current dose; monitor as clinically indicated
Grade 3	Step 1. Interrupt pazopanib . Step 2. Initiate and monitor anticoagulation as clinically indicated. Step 3. Resume pazopanib at reduced dose only if all of the following criteria are met: 
 • The subject must have been treated with anticoagulant at the desired level of anticoagulation for at least one week. • No Grade 3 or 4 or clinically significant Grade 2, hemorrhagic events have occurred while on anticoagulation treatment. Subject should be monitored as clinically indicated during anticoagulation treatment and after resuming study treatment. When treating with warfarin, international normalized ratio (INR) should be monitored within three to five days after any change in pazopanib dosing (eg, re-initiating, escalating/de-escalating, or discontinuing pazopanib), and then at least weekly until the INR is stable. The dose of warfarin (or its derivatives) may need to be adjusted to maintain the desired level of anticoagulation
Grade 4 and/or PE	Discontinue pazopanib and continue follow-up per protocol.
Arterial Thrombosis/Ischemia	
Any Grade	Discontinue pazopanib and continue follow-up per protocol.
Thrombocytopenia: Investigate and document underlying cause	
Grade 1 or 2	Continue pazopanib with current dose; monitor as clinically indicated.
Grade 3 or 4	Step 1. Interrupt pazopanib until toxicity resolves to \leq Grade 2.

	Step 2. Restart pazopanib dose-reduced by 200 mg and monitor as clinically indicated. If no recovery to \leq Grade 2 or recurrent Grade 3 or 4 thrombocytopenia, discontinue IP and follow-up per protocol.
Anemia: No specific dose reduction rules are indicated for anemia unless due to hemorrhage or bleeding as noted above.	
Palmar-plantar Erythrodysesthesia Syndrome	
Grade 1 Minimal skin changes or dermatitis without pain (erythema, oedema, hyperkeratosis)	1. Continue pazopanib at present dose
Grade 2 Skin changes with pain; limiting instrumental activities of daily living (ADLs) (peeling, blisters, oedema, bleed, hyperkeratosis)	1. Hold pazopanib 2. Treat as clinically appropriate 3. Upon resolution to Level 1 or better restart pazopanib with a dose reduction to dose level -1 (if it was a full dose[800mg]) or one dose lower than the patient was receiving prior to developing the skin changes. 4. If recurrent consider a further dose reduction by 1 dose level until dose level -2. If patient has a Grade 2 toxicity on dose level -2, then consider stopping the drug.
Grade 3 Severe skin changes with pain and limiting self care ADLs	1. Discontinue pazopanib
Other Clinically Significant Adverse Events^a	
Grade 1	Continue pazopanib ; monitor as clinically indicated.
Grade 2 or 3, if clinically significant	Step 1. Interrupt pazopanib until toxicity resolves to \leq Grade 1. Step 2. Restart pazopanib dose-reduced by 200 mg(1 dose level) and monitor as clinically indicated.
Grade 4	Discontinue pazopanib and continue follow-up per protocol.

- a. AEs are graded according to NCI Common Terminology Criteria for Adverse Events v4.0 (NCI CTCAE v3)
- b. If ECHO does not show LVEF recovery after 2 weeks, repeat ECHO 2 weeks later.
- c. Symptoms may include: dyspnea, orthopnea, and other signs and symptoms of pulmonary congestion and edema.
- d. Hypertension detected in two separate readings during up to three consecutive visits
- e. Well-controlled blood pressure defined as SBP <140 mm Hg and DBP <90 mm Hg in two separate readings during up to three consecutive visits.
- f. Symptomatic hypertension defined as hypertension aggravated by symptoms (e.g., headache, light-headedness, vertigo, tinnitus, episodes of fainting) that resolve after the blood pressure is controlled within the normal range.
- g. Persistent hypertension is defined as asymptomatic hypertension after initially successful anti-hypertensive intervention.

